Clinical relapse is the main clinical expression of RMS that constitutes up to 50% of this study population and will therefore be assessed due to its clinical importance and in an attempt to collect additional efficacy data. Although all enrolled RMS participants will be expected to be stable on their DMTs, MS relapses may occur. Thus, relapse data will be carefully collected and their impact on the primary endpoint will be assessed.

Clinical outcome assessments are considered important for understanding the impact of treatment on function and wellbeing (21). In both progressive and relapsing MS, the increasing limitation and loss of physical function are prevalent and among the most debilitating signs and symptoms of the disease (22). Physical function limitations are associated with decrements in quality of life due to diminishing productivity and ability to perform daily activities, maintain employment, and maintain social roles and emotional wellbeing. Reduction of disease impact on patient-reported physical function is therefore important to assess in addition to the clinician assessment and constitutes a direct measure of treatment effectiveness, ie, whether a treatment influences how a participant feels or functions (23).

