All MS relapses must be reported on the MS relapse eCRF page. Multiple sclerosis relapse should not be reported as an AE unless, in the judgment of the Investigator, it is unusually severe or medically unexpected, or matches the definition of an SAE.

Safety laboratory tests are optional for the unscheduled assessment visit if no intercurrent disease is suspected. If any intercurrent disease is diagnosed, it will be reported as an AE as per the safety reporting rules.

The participant will be also asked to report possible relapse symptoms during scheduled quarterly visits. If relapse is suspected, the above decision-making and reporting rules apply.

8.1.5 *Timed 25-foot walk test*

As part of the Multiple Sclerosis Functional Composite (MSFC), the T25-FW test is currently the most widely implemented method to objectively quantify gait disability in clinical MS trials. The T25-FW test is developed to quantify changes in gait of MS patients; 1 task is completed, and the amount of time required depends on each patient.

The T25-FW test will be used to assess a participant's walking ability. The participant is directed to one end of a clearly marked 25-foot course and is instructed to walk 25 feet as quickly as safely possible with several repetitions ([25](#), [26](#)). The mean walk time will be used for assessment of the participant's walking ability. An increase of >20% from the baseline score in the T25-FW test is considered as meaningful worsening ([27](#)). The Examining Investigator/rater will perform this test.

8.1.6 9-Hole Peg Test

The 9-HPT will be used to assess a participant's manual dexterity and fine motor skills. This is a PerfRO tool (performance outcome). A participant will be asked to place pegs into holes and remove them with the dominant and non-dominant hand for several repetitions (26). The mean time to test completion will serve as an assessment of the participant's hand dexterity. An increase of >20% from the baseline score in the 9-HPT is considered meaningful worsening (27). The Examining Investigator/rater will perform this test.

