8.3.7 Multiple sclerosis relapse reporting

Multiple sclerosis relapses will be exempt from being reported as AEs except when they meet the definition of a SAE or are unusually severe or medically unexpected. Hospitalization for MS relapse, if done routinely at the site (eg, for high dose IV methylprednisolone administration), will not be considered as a seriousness criterion for this study.

Data for MS relapses will be collected on the eCRF and be analyzed as part of the efficacy analysis. Other worsening of neurological symptoms that do not meet the definition of MS relapse will be reported as AEs according to general safety reporting rules.

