3.3.2 Main analytical approach

All secondary efficacy endpoints in Part A and Part B will be analyzed using the randomized and treated population. Participants who permanently discontinue the IMP or permanently modify the background DMT will be asked and encouraged to stay in the study for the remaining visits. In this case, all measurements collected after the treatment status change during the planned treatment periods will be included in the analysis.

Categorical endpoints with count data

Categorical endpoints with count data include:

Part A

- Average number of new gadolinium- (Gd-) enhancing T1-hyperintense lesions per scan from randomization to Week 48
- Annualized rate of new/enlarging T2-hyperintense lesions from randomization to Week 48
- Annualized relapse rate (ARR) of RMS population (relapsing SPMS and RRMS) from randomization to Week 48

Part B

- Number of new gadolinium- (Gd-) enhancing T1-hyperintense lesions from Week 48 to Week 96
- Annualized rate of new/enlarging T2-hyperintense lesions from Week 48 to Week 96
- ARR of RMS population (relapsing SPMS and RRMS) from randomization to Week 96

A negative binomial regression model with robust variance estimation will be used to analyze these categorical endpoints with count data. The robust variance can be estimated by specifying the participant identifier in the repeated statement using SAS PROC GENMOD (version 9.4 or later).

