For ARR of RMS population (relapsing SPMS and RRMS), a similar negative binomial regression model will be used. The model will include the total number of relapses per participant occurring in the planned treatment period as the response variable, with treatment group as the covariate. Log transformed observation duration from randomization to Week 48 for participants complete Part A, or from randomization to the last contact date for participants discontinued in Part A will be the offset variable for the ARR of RMS population in Part A. Log transformed duration from randomization to Week 96, except when a participant withdraws early from the study, in which case, the log transformed duration from randomization to the last contact of the participant before Week 96 will be the offset variable for the ARR of RMS population in Part B. The estimated ARR for each treatment group and corresponding 2-sided 95% CI will be derived from the negative binomial model where the adjusted mean value within treatment group is based on population weight. The relative reduction in ARR with SAR443820 compared to placebo, its 2-sided 95% CI and p-value will be provided.

Time-to-event endpoints

Time-to-event endpoints defined in Part A include:

- Time to onset of 12-week CDP from baseline as assessed by the EDSS score
- Time to onset of sustained 20% increase in 9-HPT confirmed over at least 12 weeks
- Time to onset of sustained 20% increase in T25-FW confirmed over at least 12 weeks

Time-to-event endpoint defined in Part B include:

- Time to onset of 24-week CDP from baseline as assessed by the EDSS score
- Time to onset of sustained 20% increase in 9-HPT confirmed over at least 24 weeks
- Time to onset of sustained 20% increase in T25-FW confirmed over at least 24 weeks
- Time to onset of CCDP, confirmed over at least 24 weeks (6-month CCDP), by the EDSS Plus composite (EDSS score increase, or 20% increase in the T25-FW test, or 20% increase in the 9-HPT)

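### Ordinary relapses in PPMS and non-relapsing SPMS are kept out of the adverse event tables, and no visible SAP output counts them by arm

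*SAP*

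**What the plan says.** **Collection.** Protocol 8.1.4.2 requires that "All MS relapses must be reported on the MS relapse eCRF page". The relapse definition in 8.1.4.1 and the rescue provision in 6.8.1 apply to all participants, whatever their MS subtype.

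**Exemption.** Protocol 8.1.4.2 states that "Multiple sclerosis relapse should not be reported as an AE unless, in the judgment of the Investigator, it is unusually severe or medically unexpected", or is an SAE. Section 8.3.7 repeats the rule: "Multiple sclerosis relapses will be exempt from being reported as AEs except when they meet the definition of a SAE". The same exceptions for severity and unexpectedness are made there. If a site routinely admits patients for relapse, that admission "will not be considered as a seriousness criterion for this study".

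**Where relapses are to be reported.** Section 8.3.7 continues: "Data for MS relapses will be collected on the eCRF and be analyzed as part of the efficacy analysis". It sets no limit by subtype.

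**What the SAP analyses.** For Part A, SAP 3.3.2 lists "Annualized relapse rate (ARR) of RMS population (relapsing SPMS and RRMS) from randomization to Week 48". The Part B endpoint covers the same population to Week 96. The model text reads "For ARR of RMS population (relapsing SPMS and RRMS), a similar negative binomial regression model will be used". Section 3.3.2 closes by ruling out sensitivity and subgroup analyses of the secondary endpoints.

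**The concern.** The protocol commits to analysing relapse data as efficacy for everyone, and the SAP carries this out only for RRMS and relapsing SPMS. For a participant with PPMS or non-relapsing SPMS, an ordinary relapse is recorded on the eCRF, is not an adverse event, and is outside the annualised relapse rate (ARR) population.

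The rules also produce an odd ordering. Under Protocol 8.3.7, neurological worsening that falls short of the relapse definition is an adverse event and is tabulated by arm. In these subtypes an event that meets the full definition may be tabulated nowhere.

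At stake is whether the study report can say how many clinical relapses occurred in each arm across the whole trial. As planned, it can say so only for the RMS subset.

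**Working it through.** No figure in the plan depends on this point, so there is none to reproduce. The check is a trace through the text, followed by an indication of scale.

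**Trace of an ordinary relapse, by MS type**

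| Step | RRMS, relapsing SPMS | Non-relapsing SPMS, PPMS |
|---|---|---|
| Relapse eCRF page (Protocol 8.1.4.2) | Yes | Yes |
| Adverse event tables and listings (Protocol 8.3.7; SAP 3.6.2) | No, exempt | No, exempt |
| ARR, Part A and Part B (SAP 3.3.2) | Yes | No |
| Further analyses of secondary endpoints (SAP 3.3.2) | None planned | None planned |
| Baseline tables (SAP 5.3) | Pre-study relapse history only | Pre-study relapse history only |
| Any other visible relapse count | None needed | None found |

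SAP 3.2.3, the sensitivity analysis of the primary endpoint, is redacted. It concerns sNfL. Protocol 3.1.1 says the impact of relapses on the primary endpoint will be assessed, so that section may use relapse data. Nothing visible shows that it tabulates relapses.

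**How many participants**

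- Protocol 3.1.1: "Clinical relapse is the main clinical expression of RMS that constitutes up to 50% of this study population". With RMS at exactly half, the number outside RMS is 0.50 × 168 = 84.
- Protocol 1.1 requires at least 50% progressive MS and counts all SPMS, including relapsing SPMS, towards that minimum. SAP 3.2.5 and 3.3.2 place relapsing SPMS in RMS. The recruitment minimum therefore sets no floor for the group outside RMS. The true number could be below or above 84.

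**How many relapses (illustration)**

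The documents give no relapse rate outside RMS. I assume 0.02 to 0.10 per year and full follow-up.

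Person-years = n × weeks × 7 / 365.25. Expected relapses = person-years × assumed rate.

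| Participants outside RMS | Weeks | Person-years | Relapses at 0.02 | Relapses at 0.10 |
|---|---|---|---|---|
| 84 | 48 | 77.3 | 1.5 | 7.7 |
| 84 | 96 | 154.5 | 3.1 | 15.5 |
| 42 | 48 | 38.6 | 0.8 | 3.9 |
| 42 | 96 | 77.3 | 1.5 | 7.7 |

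The 42-participant rows show the effect of halving the group. All counts are for both arms together.

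**The case against.** The RMS restriction is deliberate. It appears consistently in the endpoint lists of both documents, and it suits a rate model because relapses elsewhere are expected to be few. The endpoint is labelled as an RMS endpoint, so no trial-wide statement about relapses is planned. This stands, and it is a reason to leave the model alone. It does not meet the unrestricted statement in Protocol 8.3.7.

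A reader might infer that inflammatory activity triggered by the drug in progressive MS would go unseen. The documents do not support that:

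- New Gd-enhancing lesions, new or enlarging T2 lesions, EDSS progression, 9-HPT and T25-FW are analysed in all randomised and treated participants (SAP 3.3.2).
- sNfL has a planned subgroup of non-relapsing SPMS plus PPMS (SAP 3.2.5).
- Rescue treatment must be recorded (Protocol 6.8.1), and concomitant medications are summarised (SAP 5.3).

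None of these is a count of relapses by arm, but together they mean that a signal would not be hidden.

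The exemption also has exits. An investigator could judge a relapse in a participant with PPMS to be medically unexpected, and it would then be an adverse event. That depends on individual judgement, so it cannot replace a count.

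The listed risk of immunomodulatory effects (Protocol 2.3.1) should not be used to strengthen the point. It rests on animal findings considered non-adverse, and the text does not connect it with relapse. Nor does Protocol 8.3.7 say that relapses are exempt because they are analysed as efficacy. It states the two things one after the other.

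**Conclusion.** The point holds as a gap in reporting. On the visible text, ordinary relapses in PPMS and non-relapsing SPMS have no planned count by treatment group, although the protocol says relapse data will be analysed without limiting this by subtype.

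The size is about 84 of 168 participants if RMS is half of the trial. A reader might take 84 as a minimum, but the two documents classify relapsing SPMS differently and neither fixes the number outside RMS. The relapses themselves are probably few: between about 1.5 and 7.7 in Part A for 84 participants, under the assumed rates.

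Nor does the gap bias the primary analysis. sNfL at Week 48 is modelled in all subtypes, and the missing table does not alter that model. The conclusion also assumes that redacted SAP 3.2.3 contains no relapse table. If it contains one by arm and MS type, the point falls away to that extent.

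**What to change.** Keep the RMS ARR model as written. In SAP 3.3.2, add a descriptive table of on-study relapses for the randomised and treated population, giving:

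- the number and percentage of participants with at least one relapse;
- the total number of relapses;
- the crude annualised rate (relapses divided by person-years, with follow-up defined as for the ARR offset).

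Present these by treatment group and MS type (RRMS, relapsing SPMS, non-relapsing SPMS, PPMS), for Part A and for Part A + Part B, with a participant listing.

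The cost is a paragraph of SAP text, one table and one listing. The relapse eCRF page and the four-level MS type in SAP 5.3 already exist, so no new data, tests or change to reporting rules at sites are needed. The drawback is small counts in the progressive types, so the table should be descriptive only.

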1 INTRODUCTION

1.1 STUDY DESIGN

Study ACT16753 is a Phase 2, randomized, double-blind, placebo-controlled, 2 parallel-arm study evaluating the effect of SAR443820 on serum neurofilament light chain (sNfL) levels in participants with multiple sclerosis, followed by an open-label, long-term extension period.

The study consists of 2 parts (A and B) as follows:

Part A is a 48-week, double-blind, placebo-controlled part, preceded by a screening period of up to 4 weeks before Day 1.

- The screening period will be up to 4 weeks and is designed to evaluate suitability for participation in the study in terms of MS diagnosis, clinical status based on EDSS, and safety screening evaluations. No IMP will be administered in this period.
- The double-blind treatment period will have a total duration of 48 weeks for each participant and will include the following:
 - Participants will be randomized at 1:1 ratio to receive SAR443820 20 mg QD (n = 84) or matching placebo QD (n = 84).
 - Randomization will be stratified by MS clinical subtypes (ie, RRMS, SPMS, or PPMS) in order to ensure a balance between the treatment and placebo arms within each MS clinical subtype. Participants will attend in-clinic study assessments at baseline (Day 1) and Weeks 2, 6, 12, 24, 36, and 48.

All participants who successfully completed Part A will be offered to rollover to Part B.

Participants who discontinue IMP during Part A, or who choose not to enter Part B will have their early discontinuation or safety follow-up visit, respectively, up to 2 weeks after the last dose of IMP.

Part B is an open-label, long-term extension of Part A. Part B starts from the end of Part A (Week 48) and continues up to Week 96.

- The assignment of participants to study intervention in Part A will remain double-blinded during Part B unless there is medical need to unblind the study intervention assignment.
- All participants will receive 20 mg QD SAR443820 in Part B.
- Participants will attend in-clinic study assessments at Weeks 52, 72, and 96 (and Week 48 which is the last visit of Part A and first visit of Part B); Week 50, 54, 56, 58, 60, 62, 64, 66, 68, 70, 76, 80, 84, 88, 92 visits for liver chemistry only may be conducted at local labs where available.

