PPMS), visit (Weeks 12, 24, 36, 48), treatment-by-visit interaction, log-transformed baseline sNfL levels and log-transformed baseline sNfL levels-by-visit interaction. An unstructured covariance structure will be used to model the within-subject errors. The Kenward-Roger (1) approximation will be used to estimate denominator degrees of freedom and adjust standard errors. Missing data will be handled by MMRM under the missing at random (MAR) assumption. The geometric mean ratios of sNfL levels at Week 48 relative to baseline in each treatment group, as well as the ratio of the geometric mean ratios under treatment with SAR443820 compared to placebo will be estimated (point estimates and 2-sided 90% confidence intervals [CI], respectively) from the MMRM model using weights for each stratum equal to the overall proportion of participants in each stratum (ie, “population weight”) through exponentiated least squared means and exponentiated least squared means differences. Plots of geometric mean ratios of sNfL levels relative to baseline in each treatment group with 90% CIs over time will be provided.

If this MMRM model fails to converge, the following variance-covariance structures will be tested in this order:

- Heterogeneous Toeplitz
- Heterogeneous AR(1)
- Heterogeneous CS
- Toeplitz
- AR(1)
- CS.

The first (co)variance structure yielding convergence will be used as the primary analysis. When a variance-covariance structure other than unstructured is used, the denominator degree of freedom will be estimated using the between within method (DDFM=BW in SAS PROC MIXED) (2)

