For analyzing the average number of new gadolinium- (Gd-) enhancing T1-hyperintense lesions per scan and annualized rate of new/enlarging T2-hyperintense lesions, the model will include the total count of the respective type of lesion across all scheduled MRI scans during the observation duration as the response variable, with treatment group, baseline lesions count and MS clinical subtype (RRMS, SPMS, or PPMS) as covariates. For Part B endpoints, the baseline lesions count will be replaced by the Week 48 lesions count. The offset variable will be the log transformed number of MRI scans during the observation duration for T1 lesions and log transformed observation duration for T2 lesions. The observation duration for Part A is from randomization to the last MRI scan on or prior to Week 48. The observation duration for Part B is from the end of Week 48 to last MRI scan on or prior to Week 96. The average number of lesions per scan (95% CI) for Gd-enhancing T1-hyperintense lesions and the annualized rate (95% CI) of new/enlarging T2-hyperintense lesions for each treatment group will be estimated from the model along with the relative risk (95% CI, p-value) for SAR443820 compared to placebo. The adjusted mean value

within treatment group is based on a sample size dependent weight within each categorical covariate (ie, weight by overall proportion of participants in each stratum or categorical factor, also called “population weight”).

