These time to event endpoints will be analyzed by a Cox proportional hazards model. The covariates included in the model are treatment group and MS clinical subtype (RRMS, SPMS, PPMS). The hazard ratio between treatment groups, its 95% confidence interval and the p-value will be estimated from this model with robust variance estimation (6). Comparison between treatment groups will also be assessed by a log-rank test stratified by MS clinical subtype (RRMS, SPMS, PPMS). Kaplan-Meier (KM) plots of the cumulative incidence rate will be provided by treatment group to depict the course of occurrence of event over time. The proportion of participants with events at given time points (eg, 12, 24, 36, 48, etc.) will be calculated using the KM estimates.

Continuous endpoints

Continuous endpoints include:

Part A

- Change from baseline in EDSS score at Week 48
- Change from baseline in 9-HPT at Week 48
- Change from baseline in T25-FW at Week 48
- Percent change from baseline in BVL at Week 48
- Change from baseline in the volume, number, and normalized T1 intensity of SELs at Weeks 12, 24, 36 and 48
- Change from baseline in the number of PRL at Weeks 12, 24, 36 and 48.

Part B

- Percent change from baseline in BVL at Week 96
- Change from baseline in the volume, number, and normalized T1 intensity of SELs to Week 96
- Change from baseline in the number of PRL at Week 96
- Change from baseline in EDSS at Week 96
- Change from baseline in 9-HPT at Week 96
- Change from baseline in T25-FW at Week 96
- Change from baseline in MSIS-29v2 physical and psychological domains score at Week 96
- Change from baseline in MSWS-12 at Week 96

Summary statistics including mean, standard deviation, median, interquartile range (Q1, Q3), minimum, and maximum will be provided for these continuous endpoints at scheduled visits. Only non-missing data will be included. For change/percent change from baseline, only participants with baseline and at least one post-baseline assessment will be summarized.

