Normalized T1 intensity of SELs may be explored using linear mixed model. The model will include the treatment group (SAR443820 or placebo), MS clinical subtype (RRMS, SPMS, or PPMS), time (from randomization to the date of MRI sample being collected), treatment-by-time interaction, baseline value of normalized T1 intensity of SELs as the fixed effects. Both intercept and the coefficient for time are assumed to have participant-level random effects and these two random effects are assumed to be independent.

The other continuous endpoints will be analyzed using a similar MMRM approach as described for the primary endpoint of Part A in [Section 3.2.2.1](#), except that the log-transformed baseline sNfL levels will be replaced by the baseline values of the corresponding endpoint. Appropriate transformation will be used if necessary (eg, log-transform). Plots of least squares means

(\pm standard error) over time will be provided. Plots of mean (\pm SE) and/or mean change (\pm SE) over time will also be provided.

No sensitivity or subgroup analyses will be conducted.

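### Does the relapse-rate model need MS clinical subtype, given that its arm means are described as population-weighted?

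*SAP*

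**What the plan says.** SAP 3.3.2 introduces the ARR model as similar to the negative binomial model just given for lesion counts, then restates its contents: "the total number of relapses per participant occurring in the planned treatment period as the response variable, with treatment group as the covariate", with log observation time as the offset. Each arm's ARR is "derived from the negative binomial model where the adjusted mean value within treatment group is based on population weight".

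The SAP explains population weight in two other places. For lesion counts, the adjusted mean "within treatment group is based on a sample size dependent weight within each categorical covariate". For the primary sNfL analysis (SAP 3.2.2.1), estimates are formed "using weights for each stratum equal to the overall proportion of participants in each stratum".

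The other efficacy models carry subtype. Lesion counts are modelled "with treatment group, baseline lesions count and MS clinical subtype (RRMS, SPMS, or PPMS) as covariates". The Cox models and the stratified log-rank test use subtype. For continuous endpoints, "The other continuous endpoints will be analyzed using a similar MMRM approach as described for the primary endpoint of Part A", and that model includes subtype. Randomisation is stratified by RRMS, SPMS and PPMS (SAP 1.1). The ARR set is RRMS plus relapsing SPMS. Protocol 9.2.3 describes lesion-count models only, so the SAP alone specifies the ARR model.

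**The concern.** Two things look wrong.

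- **Subtype is missing.** The ARR set draws on two randomisation strata, and subtype appears in the SAP's other efficacy models. The version history shows that the sNfL and lesion models were deliberately moved to the stratification factor. ARR is not mentioned there, and no reason is given for leaving subtype out.
- **The weighting instruction has no object.** Population weight averages over strata or categorical factors, and this model has neither. Arm ARRs described as adjusted means would be unadjusted model rates. Two programmers might also deliver different analyses: one takes the covariate list literally, while the other reads the reference to a similar model and the weighting phrase as carrying subtype over from the lesion model.

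At stake would be the precision and error rate of the rate ratio, which is reported with a 95% CI and p-value in both parts, and the meaning of the arm ARRs.

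**Working it through.** **1. What the weighting phrase does under the model as written.** The model is log(rate) = b0 + b1 x treatment. For any subtype weight w, the weighted placebo mean is exp[w b0 + (1 - w) b0] = exp(b0), and the SAR443820 mean is exp(b0 + b1). In a test data set, weights of 0.5, 0.8 and 0.95 all gave 0.2162 and 0.3931 for the two arms. The phrase is redundant and yields no wrong number.

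**2. How much variance subtype could explain.** The documents give no relapse rate and no count of relapsing SPMS, so the inputs are assumed: 25% of the set is relapsing SPMS with half the RRMS rate, dispersion is 0.3, follow-up is 48/52 = 0.923 years, and the overall control ARR is 0.15, 0.25 or 0.35. Dropout is ignored.

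Let m be the mean count. The RRMS mean is r = m/0.875, because 0.75 + 0.25 x 0.5 = 0.875. Then:

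- between-subtype variance = 0.25 x 0.75 x (0.5r)²
- overdispersion = 0.3 x [0.75r² + 0.25(0.5r)²]
- total = m + overdispersion + between-subtype variance

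| ARR | m | r | Between | Total | Share |
|---|---|---|---|---|---|
| 0.15 | 0.1385 | 0.1582 | 0.00117 | 0.1457 | 0.8% |
| 0.25 | 0.2308 | 0.2637 | 0.00326 | 0.2510 | 1.3% |
| 0.35 | 0.3231 | 0.3692 | 0.00639 | 0.3627 | 1.8% |

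Removing a share of 0.8% to 1.8% of the variance lowers an SD by roughly half that, 0.4% to 0.9%, before the cost of estimating the extra term.

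**3. Simulation of the rate ratio.** Assumed: 63 RRMS and 21 relapsing SPMS, dispersion 0.3, 17% dropout (the SAP's figure), robust variance, 4,000 trials per cell.

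- Adding subtype changes the sampling SD of the log rate ratio by -0.6% to +0.8% over 30 cells covering Parts A and B.
- With a subtype effect of x0.5, Part A power at a rate ratio of 0.5 goes from 5.1% to 5.1%, 15.2% to 15.8% and 24.9% to 25.0% for the three control rates. Pure-noise covariates do as well: 4.5% to 5.0%, 15.7% to 16.2% and 26.3% to 27.1%.
- Null rejection moves by -0.3 to +0.4 percentage points. The Monte Carlo standard error of a 5% rate is 0.34 points.

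A second set of assumptions (84 RRMS, 20 relapsing SPMS, RRMS ARR 0.30, SPMS ARR 0.10 to 0.30, dispersion 0.5) agrees. Type I error is 0.049 without subtype and 0.049 to 0.054 with it. The log rate ratio moves by 0.025 to 0.039 on average.

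**4. The arm rates.** In the first set, weighting rates over subtype moves the control ARR by a median of 0.6% to 1.6%, and by 3.9% to 7.8% at the 95th percentile. The null SDs of the log ratio for Part A are 0.734, 0.579 and 0.495. Dividing by √2 gives about 0.52, 0.41 and 0.35 per arm. A 1.6% shift is then at most 0.016/0.35 = 0.05 SE, and a 7.8% shift at most 0.078/0.35 = 0.22 SE.

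In the second set, placebo ARR falls from 0.265-0.301 to 0.245-0.293. Much of that is a change of definition, because the weights there act on log rates. With true rates of 0.30 and 0.10 and weights 84/104 and 20/104, the arithmetic mean is 0.262 and the geometric mean is 0.243. The treatment-only model stays close to the former.

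**5. What adding subtype would cost.** With an effect of x0.5, one subtype has no relapse in 4% to 32% of simulated Part A trials and 0.2% to 16% of Part B trials. The term is then not estimable, and the fitted model would depend on the data.

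**The case for a change.** The strongest case for a change rests on the text alone. A SAP should admit one reading, and this paragraph admits two. Calling the model similar to the lesion model and invoking population weight both point to subtype being included; naming treatment as the covariate points away from it. ARR is a listed secondary endpoint in both parts, the variable is already collected, and the remedy is one term or one deleted phrase.

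The ambiguity stands. The argument from consistency carries less weight. The sNfL, lesion and time-to-event models cover all three subtypes, whereas the ARR set already excludes PPMS and non-relapsing SPMS. Relapsing status within SPMS was not a stratification factor, so the set is one whole stratum plus an unstratified part of another. A parsimonious model for a sparse count in that subset is a fair choice. The covariate list is also the more specific statement, so an analyst following the text fits treatment only and finds that the weighting phrase does nothing.

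**Conclusion.** The observation about the wording is correct, but no change to the plan follows. Under randomisation the treatment-only model gives a valid rate ratio. Its arm rates are well defined, and the population-weighted mean simply equals the model's arm rate. Adding subtype shows no gain in precision, power or type I error: SD change of -0.6% to +0.8%, null rejection change of -0.3 to +0.4 points. It would bring uniformity with the other models at the price of a fallback rule for a subtype without relapses. The other reading, with subtype carried over, would move the log rate ratio by only a small fraction of its standard error, so the conclusion holds whichever was meant.

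These sizes rest on assumed relapse rates, dispersion, subtype effect and number of relapsing SPMS participants, none of which the documents give. That the weighting phrase is inert needs no assumption. ARR is not among the main secondary endpoints in the Protocol synopsis and no multiplicity adjustment applies, so no confirmatory claim depends on the choice. Stating in the report which model was fitted is enough.
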